6.6. Multiple Adverse Events

The algorithm for collapsing multiple records of select AE is using the following conventions. For each patient and specified category, the corresponding adverse event records will be collapsed when:

Multiple adverse event records have the same onset date.

The onset date of an event record is either the same day or 1 day later than the resolution date of a preceding event record (contiguous events).

The onset date of an event record is after the onset date and prior to or on the resolution date of a preceding event record (overlapping events).

6.7. Other Data Handling Rules

Missing data will not be imputed in listings. The listings will only present the data recorded on the original CRF.

If an AE has a completely missing onset date, then the AE will be considered an on-treatment AE. A medication with a completely missing start date is considered a prior medication. A medication with a completely missing stop date is considered a concomitant medication.

If an adverse event or a medication has a partial missing start date or stop date, the following rules will be used to determine whether it is an on-treatment AE, or a prior or concomitant medication.

Table 14. Partial Date Imputation Rule for AE or Medication

Partial Missing Start or Stop Date	Derived Start Date	Imputed Stop Date
Missing month and day, and the year is present	January 1 of that year or first dose date if the year is the same as the year of first dose date	December 31 of that year
Missing day, but year and month are present	First day of that month or first dose date if the year and month are the same as the year and month of first dose date	Last day of that month
Missing month, but year and day are present	Missing month derived as January or same as first dose month if the year is same as the year of first dose.	Missing month imputed as December

A date with missing year will be considered as completely missing date, no imputation rule will be applied.

The rule in Table 14 is also used for determining the cycle of adverse event and concomitant medication. The derived date is used for determining AEs, the cycle of adverse event and concomitant medication.

For medical history, pre-study surgery, prior radiotherapy, and prior systemic anticancer therapies, a partial missing start date will be imputed as below:

- Missing year - no imputation, date left missing
- Missing day and month - January 1 will be assigned to the missing fields.
- Missing month only - Treat day as missing and replace both month and day with January 1.
- Missing day only - Assign the first day of the month to the missing day.

Note: additional rules for prior systemic anticancer therapies may apply as they pertain to checking for protocol violations

For medical history, pre-study surgery, prior radiotherapy, and prior systemic anticancer therapies, a partially missing stop dates will be imputed as below:

- Missing year - no imputation, date left missing
- Month is missing and year is prior to year of first dose of study drug- impute 'December'.
- Month is missing and year is the same as the year of the first dose of study drug - impute same month as in first dose date of study drug.
- Day is missing - impute 'last day of that month'. If results in a date \geq the date of the first dose of study drug impute day as the day prior to date of first dose of study drug.

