5.3.4.2. Concomitant Medication and Therapy

Medications started prior to the first dose of study drug and continued into the treatment period are considered as concomitant medications and therapies. Medications taken on or after the first dose of study drug through 30 days after the last dose of study drug are considered as concomitant medications and therapies.

Concomitant medications will be coded with World Health Organization (WHO) Drug Dictionary (most up-to-date version at the time of analysis). Concomitant medications will be summarized by ATC level 2 (Therapeutic Main Group) and ATC level 4 (Chemical/Therapeutic Subgroup) for each cohort and for all patients based on All Treated Population. Medications will be sorted in descending order of frequency of ATC level 2 and ATC level 4 within ATC level 2 in the total column. A patient will be counted only once within each level of summarization if the patient has taken a medication more than once. Agents and medications will be reported using the generic name. All concomitant medications will be listed.

In addition, the number and percentage of patients who received concomitant medications for management of hyperphosphatemia will be summarized by medication class and generic term for each cohort and for all patients. Total duration of medications (excluding overlaps) for management of hyperphosphatemia will be also summarized.

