6.2. Post-Baseline Period

To allow differentiation as to which study period an Adverse Event occurred, three categories are defined based upon onset date. Adverse Events that had onset dates prior to the first dose of study drug are considered "prior". Adverse events with onset dates on or after the first dose of study drug and within 30 days following the last dose of study drug are considered "**on-treatment**" or equivalently "**treatment emergent**". Events with onset dates more than 30 days after the last dose of study drug are considered as "post-treatment". No "subtracting rule" will be applied when an AE occurs both pre-treatment and post-treatment with the same preferred term and grade. AE summary tables will be based on on-treatment AEs only. Adverse events with onset dates prior to the first dose of study drug as well as those after the last dose of study drug +30 days will be identified in the data listings.

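### SAP 6.7 and Table 14 derive a missing AE onset without checking the stop date, so an AE that ended before first dose can be dated after its end and counted as on-treatment

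*SAP*

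**What the plan says.** SAP 6.7 sets out what happens when an AE start date is incomplete. Its stated purpose is classification: "the following rules will be used to determine whether it is an on-treatment AE, or a prior or concomitant medication". Table 14 has three rows for the start date:

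- Month and day missing: "January 1 of that year or first dose date if the year is the same as the year of first dose date".
- Day missing: "First day of that month or first dose date if the year and month are the same" as those of the first dose date.
- Month missing, day known: "Missing month derived as January or same as first dose month if the year is same as the year of first dose". The recorded day is kept.

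For a start date that is missing altogether, the rule is "If an AE has a completely missing onset date, then the AE will be considered an on-treatment AE".

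The section adds: "The derived date is used for determining AEs, the cycle of adverse event and concomitant medication". SAP 6.2 defines on-treatment by onset: "Adverse events with onset dates on or after the first dose of study drug and within 30 days following the last dose" of study drug. It also restricts the AE summary tables to on-treatment events.

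Table 14 has a column for stop dates, but it only completes a partial stop date. Nothing compares a stop date with the derived start or with first dose.

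**The concern.** Moving an uncertain onset to the first dose date is a normal conservative default. It is right when the event might have begun on treatment. When the record carries a stop date before first dose, that uncertainty is gone: the event began and ended before any study drug. The rule as written ignores this, dates the onset after the event ended, and calls the event on-treatment.

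At stake is the accuracy of the on-treatment AE summaries and of the cycle to which the event is assigned. The cohorts are small, so a single record is visible in a percentage.

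**Working it through.** The plan states no figure on this point, so there is none to reproduce. The check applies the rules as written.

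**Inputs.** Start-date rules: SAP 6.7 and Table 14. Classification: SAP 6.2. Time from consent to first dose, at most 28 days: SAP 4.1, Table 2. Cohort size, 20 to 26: SAP 3.3. Assumed for illustration: first dose 20 March 2021, AE resolved 12 March 2021 (complete stop date).

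**Step 1. Apply Table 14 and the missing-onset rule, then SAP 6.2.**

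| Recorded onset | Derived onset | Derived onset minus stop | Status |
|---|---|---|---|
| 2021 only | 20 March | 20 − 12 = 8 days | on-treatment |
| March 2021 | 20 March | 20 − 12 = 8 days | on-treatment |
| Day 25, 2021, month missing (true onset 25 February) | 25 March | 25 − 12 = 13 days | on-treatment |
| Day 2, 2021, month missing (true onset 2 March) | 2 March | 2 − 12 = −10 days | pre-treatment |
| Nothing recorded | none | not defined | on-treatment |

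Four of the five patterns are wrong. The first two rows of Table 14 err whenever the known parts match first dose and the known stop is earlier. The third errs only when the recorded day falls on or after the first-dose day.

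**Step 2. Look for a rule elsewhere that corrects it.** SAP 5.5.2.2 defines on-treatment by starting or worsening at or after first dose. SAP 6.1 defines pre-treatment AEs by onset date when times are missing. SAP 6.2 uses onset only. None says that a stop before first dose makes an AE pre-treatment. SAP 6.7 does compare an imputed stop date with first dose for medical history and prior anticancer treatment, but gives AEs no matching check.

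**Step 3. Effect on one row of a table.** One patient is 1/20 = 5.0 percentage points in a cohort of 20 and 1/26 = 3.8 points in a cohort of 26. These are upper limits: the tables count patients by worst grade, so nothing is added if the patient has a genuine on-treatment event of the same term and at least the same grade.

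**Step 4. How often the rule errs, given such a record.** Assume that true onset is uniform over the 28 days before dosing, that the AE stopped before dosing, and that first dose is uniform over a 365-day year. There are 365 × 28 = 10,220 combinations.

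- Month and day missing: the rule errs unless onset fell in the previous calendar year, which happens in 1 + 2 + … + 28 = 406 combinations. (10,220 − 406)/10,220 = 96%.
- Day missing: the rule errs when onset and first dose share a month. A 31-day month gives 462 such combinations, a 30-day month 434 and February 378. (7 × 462 + 4 × 434 + 378)/10,220 = 5,348/10,220 = 52%.
- Month missing: the rule errs when onset fell in the previous month of the same year and the derived date exists. The first condition holds in 10,220 − 406 − 5,348 = 4,466 combinations. In 193 of these the derived date does not exist: 28 + 27 + 26 = 81 for onset on 29 to 31 January with first dose in February, and 4 × 28 = 112 for onset on day 31 with first dose in a 30-day month. (4,466 − 193)/10,220 = 42%.

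These shares are conditional on such a record existing. They say nothing about how many there will be.

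**Step 5. Add the check.** With the rule that a stop before first dose makes the AE pre-treatment and bounds its start, every case in Step 1 becomes pre-treatment, with any derived start no later than 12 March. Records with a missing stop date, or a stop on or after first dose, are unchanged.

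**The case against.** The strongest reply is that such records will hardly occur. Protocol 9.1 says unrelated AEs between consent and first dose need not be recorded unless local rules require it, and treats signs and symptoms of pre-existing disease as baseline findings. Protocol 6 collects baseline signs and symptoms separately. The window is at most 28 days. Protocol 9.2.1 asks for onset and resolution dates. The listings keep the recorded dates, so an affected record can be traced. All of this stands, and it limits the frequency. It does not make the rule right when a record does occur, and AEs from screening procedures remain reportable under Protocol 6.

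SAP 6.1 also describes baseline events in general as those occurring before first dose, which fits an AE that ended by then. But its AE-specific line goes by onset date, so it does not settle the matter.

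A reader might infer more than the documents support:

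- *The AE enters every on-treatment table and is attributed to study drug.* Many tables are limited to related, serious, fatal, or discontinuation or modification events, and SAP 5.5.2.2 says that on-treatment does not imply a causal relationship.
- *Medications are misclassified in the same way.* SAP 5.3.4.2 counts as concomitant "Medications taken on or after the first dose of study drug through 30 days after the last dose of study drug", or those started earlier and carried on into treatment. A medication with a recorded stop before first dose meets neither description on its facts.
- *Negative durations disturb the collapsing rules.* SAP 6.5 and 6.6 collapse records by comparing the dates of one record with those of another. That algorithm calculates no duration.
- *Imputed stop dates let an event resolve after death.* SAP 6.7 gives Table 14 the purposes of classification and cycle. It does not say that imputed stop dates feed time to resolution.

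**Conclusion.** The point holds for AEs. As written, SAP 6.7 and Table 14 can give an AE with a recorded pre-dose stop an onset after it ended, and SAP 6.2 then counts it as on-treatment in the summaries whose other criteria it meets and in the cycle of the derived date. A completely missing onset has the same gap.

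Each such record can shift a row by up to 3.8 to 5.0 percentage points, depending on cohort size. The documents give no rate for incomplete pre-dose AE dates, so no probability of an affected table can be stated; the recording rules suggest that it is low. ORR and the other efficacy endpoints are untouched. This is a minor defect, worth correcting because the rule gives a demonstrably wrong answer and the correction is short.

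**What to change.** Add to SAP 6.7 and Table 14: if the recorded stop date of an AE, or the latest date it could be when partial, is before first dose, the AE is pre-treatment and its derived start may not be later than that stop date. Apply the same check before calling an AE with a completely missing onset on-treatment. Keep the present default when the stop date is missing or falls on or after first dose.

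The stop dates that Table 14 already imputes (end of month, 31 December, or December with the recorded day) are the latest possible dates, so the check can use them directly. No cap on imputed stop dates at death or data cut-off is needed for this. A cap at death would also sit badly with SAP 6.5, which treats resolution on the date of death as unresolved.

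The cost is a sentence or two of SAP text and minor programming. No new data are needed.

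### The missing-month row of SAP Table 14 can date a same-year adverse event before first dose and drop it from the AE summaries, while AEs with less date information are kept

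*SAP*

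**What the plan says.** SAP 6.7, Table 14, gives the derived start date for AEs and medications with partial dates. If only the month is missing, the rule is: "Missing month derived as January or same as first dose month if the year is same as the year of first dose". The row mentions neither the day nor a limit at the first dose date.

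The other two rows fall back on the first dose date itself. With month and day missing: "January 1 of that year or first dose date if the year is the same as the year of first dose date". With only the day missing: "First day of that month or first dose date if the year and month are the same as the year and month of first dose".

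For dates with less information still, the section says: "If an AE has a completely missing onset date, then the AE will be considered an on-treatment AE". It adds: "A date with missing year will be considered as completely missing date, no imputation rule will be applied". An AE without a year is therefore on-treatment too.

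The result decides classification: "The derived date is used for determining AEs, the cycle of adverse event and concomitant medication". Under SAP 6.2, "Adverse Events that had onset dates prior to the first dose of study drug are considered" prior, and "AE summary tables will be based on on-treatment AEs only". SAP 5.5.2.2 likewise summarises only on-treatment AEs and lists all of them.

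**The concern.** The section leans towards counting an AE as on-treatment whenever its date is too incomplete to tell. The missing-month row departs from that: a site that records the day as well as the year can cause the AE to be excluded, whereas the year alone would have kept it. The error runs in the unsafe direction, because an on-treatment event leaves the incidence tables. Each cohort will have 20 to 26 patients (SAP 3.3), so one patient missing from the count for a term changes its incidence by 1/26 = 3.8 to 1/20 = 5.0 percentage points.

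There is a smaller problem in the other direction. The rows that impute the first dose date do not look at a recorded stop date. An AE known to have ended before treatment can be given an onset on the first dose date, after its own end. It would then count as on-treatment. If it is an AE of special interest, its negative duration would also enter the clustering and time-to-resolution derivations of SAP 6.5.

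**Working it through.** The plan states no figure on this point, so there is none to reproduce. The check applies Table 14 as written.

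**1. Worked example.** First dose 20 June 2021.

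| Recorded onset | Derived onset | Class | In AE summaries? |
|---|---|---|---|
| Day 05, month unknown, 2021 | 5 June 2021 | prior | no |
| Day and month unknown, 2021 | 20 June 2021 | on-treatment | yes |
| Day unknown, June 2021 | 20 June 2021 | on-treatment | yes |
| Year unknown, or nothing recorded | none | on-treatment | yes |

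**2. How plausible is the date chosen?** Protocol 9.1 collects AEs from consent, and SAP Table 2 places consent at most 28 days before first dose, here 23 May. The fifth of the month falls once between 23 May and 20 June (5 June). It falls six times after first dose in that year (5 July to 5 December), provided the patient is still within the on-treatment period. The row picks the one pre-dose candidate. Protocol 9.1 also generally does not require unrelated pre-dose AEs to be recorded, so a recorded AE is more likely to be post-dose.

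**3. Share misclassified, given the first-dose day.** For first dose on day *d* of a 30-day month and a recorded day uniform on 1 to 30, the share dated before first dose is (*d* - 1)/30:
- *d* = 1: 0/30 = 0%
- *d* = 10: 9/30 = 30%
- *d* = 20: 19/30 = 63%
- *d* = 30: 29/30 = 97%

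**4. Share misclassified, over a calendar year.** Take every first-dose date in 2021 and AEs that truly start on or after first dose, with onset uniform over a window from first dose and only the month missing. The documents give no AE timing, so uniform onset is an assumption and the window is varied.

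| Window (days) | Classed as prior, among same-year AEs | Derived date does not exist |
|---|---|---|
| 30 | 45.0% | 0.01% |
| 90 | 45.2% | 1.0% |
| 180 | 44.9% | 1.3% |
| 365 | 43.8% | 1.6% |

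The last column covers cases such as day 31 placed in June. No AE with onset in a later calendar year was classed as prior, and the other two rows misclassified no truly on-treatment AE.

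**5. Known stop date.** First dose 20 June 2021, AE start day unknown in June 2021, stop recorded as 10 June 2021. The missing-day row gives an onset of 20 June, so stop minus start is 10 - 20 = -10 days. SAP 6.2 classifies by onset date alone, so the AE is on-treatment although it ended ten days before treatment began. The row for missing month and day gives the same result.

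**6. With a floor.** If the derived date in the missing-month row is the later of the imputed date and the first dose date, no truly on-treatment same-year AE can be dated before first dose. The shares in step 4 fall to 0%.

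**The case against.** The strongest reply is that this may never happen. A date with a day and a year but no month is unusual. The trial has about 46 patients, seen on Days 1, 8 and 15 of Cycle 1 and then at each cycle, and monitors query discrepancies (Protocol 12.6.2). The documents give no frequency for such records, and it could be zero. That stands, and it limits the importance of the point.

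It could also be said that a programmer would treat the day as missing. The text does not say so. For medical history and prior therapies, the same section explicitly discards the day when the month is missing; Table 14 has no such instruction. Nor does the mention of worsening in SAP 5.5.2.2 rescue the AE, because SAP 6.2 sorts AEs by onset date only.

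Three stronger readings are tempting, and the documents do not support them.

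- *The AE vanishes from the report.* It does not. All AEs are listed, those before first dose are identified in the listings, and listings show dates without imputation. Only the summaries lose it.
- *Medications stopped before treatment are counted as concomitant.* SAP 5.3.4.2 requires that the drug continued into the treatment period or was taken on or after first dose. A known stop before first dose meets neither condition. A derived start later than the stop is untidy, but it does not make the drug concomitant.
- *Nearly half of all month-missing AEs in the first-dose year are wrongly dropped.* If AE day and first-dose day are independent and uniform on 1 to 28, the chance that the AE day is earlier is 27/56 = 48%. That figure includes AEs that really did start before first dose. With a December first dose, for example, a same-year AE with an earlier day can only be pre-dose. Conditioning on true on-treatment onset gives 44-45%.

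**Conclusion.** The point holds as an inconsistency in the AE date rules, of low priority. As written, the missing-month row excludes from the summaries some AEs that would be included if less were known about their dates. The error needs three things together: only the month missing, onset in the first-dose year, and a recorded day earlier than the first-dose day. The 44-45% rests on uniform onset and on first-dose dates spread evenly over the year; for an individual patient the share runs from 0% to 97% with the day of first dose. It is a share of a group whose size is unknown and probably small, so no effect on a reported result can be claimed.

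The stop-date gap also holds, for AEs only, and it overcounts rather than undercounts.

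**What to change.** Amend SAP 6.7, Table 14, for AEs:

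1. In the missing-month row, when the year equals the first-dose year, set the derived start to the later of the imputed date and the first dose date. If the imputed date does not exist, treat the day as missing as well.
2. For all rows, if a known stop date is before the first dose date, the AE is pre-treatment and the derived start may not be later than the stop date.
3. Leave alone any AE whose recorded month or year already shows onset before first dose. With first dose on 20 June, an AE recorded as May with the day unknown stays prior even if it resolved in July. A general floor on every row would wrongly turn it into a treatment-emergent event.

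The medication rules in SAP 5.3.4.2 need no change on this account.

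The cost is a few sentences in the SAP and a small edit to the date derivation, best made before programming; no new data are needed. Change 1 will count a few truly pre-dose AEs as on-treatment when the month is missing and no earlier stop is known. The other two rows already accept that same conservative trade.

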8. CHANGES IN PLANNED ANALYSIS

There have been no changes to the initially planned analyses as of the finalization of this SAP.
